### **Exploratory Health outcomes**

The time to the occurrence of urinary tract infections and late onset sepsis will be measured from the start of the study to two weeks after study completion. Because of the small

sample size, we estimate the risk of urinary tract infections and late onset sepsis by intervention using the log rank test.

**Aim 3.** Analysis of interview transcripts will entail the review of transcripts to develop codes and the subsequent application of codes to all transcripts. Coded data will be reviewed to identify themes that characterize parents' and providers' of the acceptability and feasibility of the intervention. Data analysis activities will be supported by the use of Atlas.ti, a software program that supports the systematic coding and review of data. Rigor throughout the coding process will be maintained through a memo writing to recording thoughts, decisions, progression of code list, and identification of categories, and verifying coding results and interpretation with members of the research team.

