**Exploratory health outcomes** will examine the incidence of late onset sepsis and urinary tract infections in both bundled care groups.

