### 4. Design & Procedures

**a. Design and Setting.** A randomized controlled designed will be used to evaluate the effect of *bundled diaper care* on overall infant and skin health. Infants will be recruited from the Level IV Intensive Care Nursery (ICN) at Duke University Hospital. The ICN is a Level IV, 67-bed nursery and one of the area's leading referral centers for infants born prematurely. The

Duke ICN has an average daily census of 90% and annually admits 150 VLBW infants. The ICN practices individualized developmental care with standard bundled care intervals that vary based upon an infant's birth weight and feeding status (every 3, 4, or 6 hours). Infants who are admitted or transferred to one of the ICN three stepdown units will also be considered if eligible and will continue to receive the intervention when transferred including the Special Care Nursery at Durham Regional Hospital. The principal investigator has been a clinical nurse specialist affiliated with the ICN since 1993 and has the support of the nursery medical and nursing team to conduct this research including the Division of Neonatology, the ICN Intensive Care Developmental Care Team and the Medical Director.

**b. Participants.** A maximum of 80 VLBW infants will be recruited to ensure at least 25 infants in each study group with complete data. Ten parents of infant participants (5 in each study group) and 10 health care providers will participate in interviews about the acceptability and feasibility of the diapered bundled care intervention. The goal of this study is to enrich the literature with estimation of values and variances of the outcomes measured as well as how these values change over time. With a total sample size of 50 VLWB infants, we are confident that we will be able establish effect to inform a larger subsequent study. Because most of the infants are expected to receive care up to 6-weeks, we expect little missing data or participant attrition.

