### Infant Exclusion criteria are:

- 1. Neonatal Abstinence Syndrome
- 2. Humidified incubator
- 3. Diaper rash
- 4. Pre-existing or genetic skin conditions
- 5. Severe illness requiring 1:1 nursing care: e.g. minimal stimulation protocol, high frequency ventilation, vasopressor drug support, or body cooling.

Infants will be recruited and enrolled as soon as they meet study criteria (**see Figure 1**. **Study Schemata**). Data collection will begin following study enrollment and will continue until 6 weeks following randomization (**see Table 1**).

Figure 1. Study Schemata

c. Intervention: Infants will be randomly assigned and stratified by birth weight (≤ 800 grams, >800 grams to 1150 grams, > 1150 grams) to either 3- or 6- hour bundled diaper care. All infants will receive bundled care per unit standards until they are eligible for 3-hour bundled care. Infants typically transition to 3-hour bundled care once they are receiving interval feedings every three hours. This transition usually occurs before 3 weeks chronological age in infants >800 grams at birth and by 6 weeks

for infants ≤ 800 grams. Other care activities included in the standard 3-hour bundle vary based upon infant treatment needs, but usually include a diaper change. The only difference in a 3-hour and 6-hour bundled care event will be the timing of the diaper change. Infants will receive a diaper change at either 3 or 6 hours. While 3-hour bundled care is standard of care, this is a clinical environment in which caregiving cannot be expected to occur exactly every three hours to the minute, therefore both expected and actual times for the bundled care events will be collected to include in data analysis as needed. Infants who are receiving the 6-hour bundled diaper care will continue to receive 3-hour care interventions for all other interventions or as dictated by infant care needs. At the 3-hour caregiving interval in which the 6-hour bundled care infants are not due for a diaper change, the nurse will peek into the diaper to ensure there are no stool present. If stool is present, a diaper change should occur and the deviation from the protocol noted in the bedside documentation.

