	EMR	Stool pattern (categorical)	3x/week with observation	
	EMR	Feeding type (formula vs. breast and route; enteral	3x/week with observation	
		vs. nipple)		
	Bedside	Diaper size and brand	3x/week with observation	
	checklist			
	Stool	Scavenged	1x/week as available	
	Aim 3. Feasibility			
Intervention	Interviews	Parent perceptions	End of infant data	
acceptability			collection;	
and feasibility		Provider perceptions	At study end	
•	Exploratory Health Outcomes			
Late onset	EMR	Presence or absence	Two weeks after end of the	
sepsis			study	
Urinary tract	EMR	Presence or absence	Two weeks after end of the	
infection			study	

<sup>1EMR=electronic medical record; GA=gestational age at birth; TEWL=transepidermal water loss; NSCS=neonatal skin condition score.

- ii. Physiologic measures: Heart rate, respiratory rate, and pulse oximetry will be measured continuously with a GE Cardiopulmonary monitor (standard monitor at DUH) with acquisition from the server, sent to the PI weekly for all enrolled subjects in a data secured zip file. 1-minute values for each 24-hour observation in which a bundled care data collection occurred will be extracted and the required time frames will be extracted for analysis.
- iii. Bundled Care: The content of bundled care will be determined through the observational coding of all caregiving activities during weekly observations (3 times/week for 3-hour diapered and 4 times/week for the 4-hour diapered intervention group; see intervention section above) and 12-hour videotaping (1 time per week for each group) of bundled care events. The length of time for each bundled care event will be operationally defined as beginning when the nurse's hands enter the incubator and will end when the nurse's hands leave the incubator following caregiving.
- iv. Microbiome: One microbiome sample will be taken from the buttocks immediately after the diaper is removed and before the skin is cleaned, if there is NO stool present. A second swab will be collected from the chest at the same time. The following procedure will be used for all microbiome samples. Needed supplies will include a tube of sterile solution of PBS + 0.1%Tween 20 and a Nova Biostorage FLOQ swab with cuvette.
  - a. Remove the swab from the package
  - b. Insert the tip of the swab into the sterile PBS + 0.1% Tween 20 solution until moistened.

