### 10. Data Analysis and Statistical Considerations

Initially, we will conduct descriptive analyses, including examination of means and proportions and the measures of variability for each variable overall and by bundled care groups. The descriptive analyses will be followed by modeling approaches to respond to the research questions. Tests of statistical significance will be two-sided and the threshold for statistical significance will be P < 0.05.

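### Infection risk is to be estimated with a log-rank test because the sample is small, but that test estimates no risk, its usual P value is a large-sample one, and no between-arm difference or interval is planned

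*Combined protocol and SAP*

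**What the plan says.** Section 2 (Purpose of the Study) states that the exploratory outcomes "will examine the incidence of late onset sepsis and urinary tract infections in both bundled care groups". Section 10, under Exploratory Health outcomes, says that time to each infection is "measured from the start of the study to two weeks after study completion". It then gives the small sample as the reason for the method: "we estimate the risk of urinary tract infections and late onset sepsis by intervention using the log rank test". No Kaplan-Meier estimate, hazard ratio, risk difference, confidence interval, or exact or permutation version of the test is named for these outcomes.

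Three other places bear on this:

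- Section 10 opens by promising descriptive statistics, including proportions, for every variable by group. It adds: "Tests of statistical significance will be two-sided and the threshold for statistical significance will be P < 0.05".
- Table 1 lists each infection as "Presence or absence", taken from the medical record two weeks after the end of the study. It lists no onset date.
- Section 4b (Participants) says "A maximum of 80 VLBW infants will be recruited to ensure at least 25 infants in each study group with complete data". It describes the study's goal as estimating outcome values and their variability to inform a larger trial.

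**The concern.** The sentence asks a test to do an estimator's job. The log-rank test compares two event-time distributions and returns a statistic and a P value. It gives neither the risk in each arm nor the size of the difference.

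The stated reason also points the wrong way. The usual log-rank P value refers the statistic to a normal or chi-square distribution, and that approximation depends on the number of events. With few infections, the sample size argues for caution with this P value.

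These two infections are the only infection outcomes named in a trial that lengthens the interval between diaper changes. If the reported comparison is a P value alone, a non-significant result says almost nothing about how much added risk has been excluded. A significant one could rest on a split that an exact calculation does not support. A later trial would need the estimate and its interval.

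**Working it through.** **Inputs**

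- Infants per arm: 25, the minimum with complete data (Section 4b). The 80-infant maximum gives 40 per arm, used as a check.
- Allocation: no ratio is stated; 1:1 is assumed from 25 per group.
- Test level: two-sided 0.05 (Section 10).
- Follow-up: data collection "will continue until 6 weeks following randomization", plus two weeks. That is about 8 weeks if study completion means the end of each infant's own 6 weeks.
- Infection risk, event count, effect size and power: not given, so the plan has no figure to reproduce. Assumed range: 2% to 10% risk per infection, so 50 × 0.02 = 1 to 50 × 0.10 = 5 events.
- Simplifications: no tied event times and no censoring before the events.

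**Step 1. Log-rank P value when all events fall in one arm**

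At successive events i = 0, 1, 2, ... the share of the risk set in that arm is p_i = (25 − i)/(50 − i). With k events, Z = (k − Σp_i)/√Σp_i(1 − p_i).

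For k = 4:

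- Σp_i = 25/50 + 24/49 + 23/48 + 22/47 = 1.937
- Σp_i(1 − p_i) = 0.998
- Z = (4 − 1.937)/√0.998 = 2.065, so P = 0.039

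The exact two-sided permutation P value is 2·C(25,k)/C(50,k). For k = 4 it is 2 × 12,650/230,300 = 0.110.

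| Events, all in one arm | Log-rank P | Exact P |
|---|---|---|
| 2 | 0.153 | 0.490 |
| 3 | 0.077 | 0.235 |
| 4 | 0.039 | 0.110 |
| 5 | 0.020 | 0.0502 |

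The one-sided split is the most extreme result possible, so with 3 or fewer events the test cannot reach 0.05. The chance of 3 or fewer events among 50 infants (binomial) is 98.2% at 2% risk, 76.0% at 5% and 25.0% at 10%. At 40 per arm a 4-0 split gives 0.041 against 0.116, so recruiting to the maximum does not remove the discrepancy.

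**Step 2. False-positive rate**

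Enumerating all arm sequences under the null at 25 per arm, the nominal 5% test has these rates given the event count:

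| Events | 1–3 | 4 | 5 | 6 | 7 | 8 | 10 |
|---|---|---|---|---|---|---|---|
| Rate | 0% | 11.0% | 5.0% | 2.2% | 9.8% | 4.9% | 7.4% |

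Weighting these rates by the binomial distribution of the event count gives an average of 0.2% at 2% risk, 2.0% at 5% and 4.9% at 10%. Just outside the assumed range, at 15%, it is 5.3%.

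**Step 3. What non-significance would mean**

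Take a hazard ratio of 2 for illustration. Schoenfeld's approximation gives power ≈ Φ(½√d·ln 2 − 1.96), where d is the number of events.

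- d = 4: Φ(0.693 − 1.96) = 10%
- d = 10: Φ(1.096 − 1.96) = 19%
- 80% power needs 4(1.96 + 0.84)²/(ln 2)², or 66 events, more than the 50 infants

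**Step 4. What an estimate would show**

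Risk differences at 25 per arm with 95% Newcombe (score-based) intervals:

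| Events | Difference, points | 95% CI | Fisher exact P |
|---|---|---|---|
| 2 vs 1 | 4 | −12.6 to +21.3 | 1.00 |
| 4 vs 0 | 16 | −0.4 to +34.7 | 0.110 |
| 5 vs 2 | 12 | −8.3 to +32.0 | 0.42 |

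With no events in 25, the upper end of the exact two-sided 95% interval is 1 − 0.025^(1/25) = 13.7%.

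**The case against.** Four points can be made for the plan.

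- **Incidence is already covered.** Proportions by group are promised for every variable, and each infection is recorded as a yes/no item, so crude incidence by arm should appear. This stands. A reader might infer that the plan will produce no risk figure at all; Section 10 does not support that. What is missing is a between-arm difference and any interval.
- **The 11% rate is a worst case.** It holds only given exactly 4 events. A reader might infer that the planned test has a false-positive rate of about 11%, but averaged over event counts it does not. This also stands.
- **The reason may mean something else.** Most other between-arm comparisons of clinical and skin outcomes in Section 10 use covariate-adjusted models, so the small sample may explain an unadjusted comparison here. The plan also does not say that the P value must be asymptotic. This is a fair reading of the motive, but it leaves the test without an estimate. Unless an exact version is specified, the usual one will be run.
- **The outcomes are exploratory.** The plan bases no decision on this P value and nowhere says that non-significance would show no added risk. This limits the consequence. It does not make a bare P value more useful in a study whose goal is estimation.

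The event count could also exceed the range used here, since the documents give no infection rate.

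**Conclusion.** The point holds in a limited form. The log-rank test cannot estimate infection risk by arm, small sample size is no reason to choose it, and no between-arm estimate or confidence interval is planned for outcomes whose stated target is incidence.

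Its practical size depends on few infections occurring, which is an assumption. In that setting, a single P value can mislead at particular event counts (0.039 against 0.110 for a 4-0 split). A non-significant result is close to uninformative, and with 3 or fewer events it is certain.

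The calculations do not show overall false-positive inflation: the average rate is about 5% or less for risks of 2% to 10%. They assume 25 per arm, 1:1 allocation, untied events and no early censoring. Because the outcomes are exploratory, this is a change worth making to the analysis section and does not threaten the trial's main aims.

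**What to change.** Replace the log-rank sentence with an estimation statement. For each infection, report the risk in each arm up to two weeks after the infant's 6-week study period, and the risk difference, all with 95% confidence intervals by a named exact or score method. Draw the exploratory conclusion from the interval.

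If a P value is kept, specify an exact or permutation version. Say in advance that the interval leads, because the two can disagree at the margin: at 5 vs 0 the Newcombe interval is 2.6 to 39.1 points while the exact P value is 0.0502.

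If a time-to-event method is kept, add the date of onset to Table 1, which lists only presence or absence. Kaplan-Meier risks at the same time point could then replace crude proportions if some infants are not followed to the end.

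The cost is a little analysis work, onset dates from the medical record if needed, and a less favourable P value when events are few (0.110 instead of 0.039 for a 4-0 split). Design and sample size are unchanged.

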## **Data and Safety Monitoring**

There will be minimal risk associated with the study. The only study intervention is the timing of the diaper change. A record of study data for each subject will be maintained in the Research Office. Study records will be labeled with a code number. The key linking the identity of the subject to the code number will be separately maintained in the Research Office, under lock and key. No data that includes subjects' names, addresses, medical record number or other identifiers will leave Duke. Based upon the executed DTA with Kimberly Clark, microbiome samples will be sent via secure transfer for data analysis. The DTA will be uploaded under the full protocol section of the IRB.

## Privacy, Data Storage, and Confidentiality

Study records (hard copy and electronic) and biologic samples will be labeled with a code number to reduce the small risk of loss of confidentiality. The key linking the identity of the subject to the code number will be separately maintained in the School of Nursing Research Office, under lock and key. No data that includes subjects' names, addresses, medical record number or other identifiers will leave Duke. All data will be collected and de-identified for data analysis. Data will be downloaded into a secure file and de-identified and stored on a secure server for analyses at Duke School of Nursing. All completed study documents will be stored in the study office within Duke School of Nursing in a locked cabinet.

Microbiome samples will be processed for total genomic DNA using standardized procedures by [name] in Shallowater, TX. All samples send to [name] will be de-identified. Processed samples will be destroyed by [name] within two years of completed analysis. Unused and unprocessed samples will be stored long-term at -80°C in a locked room at in [name]'s lab.

